2020-10-04	2	
Sections 7.3 and 9: Data on physical activity and hand grip strength will be collected at all study centers, not just at those who currently have access to the necessary equipment.
 
Sections 3.3, 7.3, 9, and 13.6: Health-related quality of life outcomes have been added.
 
Section 3.3: The exploratory objective of comparing the effects of one versus two infusions has removed, as such an analysis may be biased when it is based on a comparison of more and less adherent participants.
 
Section 3.3: An exploratory objective has been added to investigate whether there is an interaction effect between zoledronic acid and FRAX score.
 
Sections 7.1-7.2: Non-vertebral fracture has been added as a secondary outcome. The outcome of fall without fracture has been redefined to include only falls from standing height or less. International Classification of Diseases codes have been included for all primary and secondary outcomes.
 
Sections 5.1 and 13.2: The definition of fall from standing height or less has been specified with ICD-10-SE codes. Falls on stairs or steps have been excluded from the definition.
 
Section 9: All baseline testing has been moved to the screening visit so that baseline data will be collected for all patients who provide written informed consent, not only for those who are eligible and randomized. This change also simplifies the randomization visit. Similarly, all testing at Visit 2 (time of second infusion) has been moved to Visit 1 to simplify Visit 2 and to ensure that follow-up data are collected on patients who withdraw from the study because of ineligibility for the second infusion.
 
Section 9: Renewal of vitamin D prescriptions may be done at every follow-up contact. Each investigator will decide whether a participant does not need a second loading dose of vitamin D because the participant has taken enough monthly vitamin D.
 
Section 13.6: The treatment-by-baseline value interaction terms have been removed from the analysis of covariance models, as their inclusion is not customary.
 
Section 13.7: Post-infusion symptoms occurring ≤ 3 days after each infusion will be presented.
 
Section 13.1: The reporting of the recruitment process has been expanded.
 
Section 6.1: Premature unblinding will not lead to automatic discontinuation of treatment.

Study Name: The Fragility Fracture Trial
 Version No: 2
 Date: 2020-10-04
 EudraCT No: 2019-004766-17

Trial statistician	
 - Write a computer program for generating a randomization list - Develop an electronic case report form (eCRF) - Continuously monitor incoming data for accuracy, completeness, and compliance with the protocol - Conduct a blind review of the trial database - Report to the sponsor when the trial database is accurate and complete - Draft the Clinical Study Report
University Hospital of Umeå Clinical Research Center	
 - Generate and store a randomization list - Monitor the trial for adherence to GCP, regulations, and ethical guidelines - Assist in reporting SUSARs - Assist in writing DSURs - Assist in developing and maintaining the eCRF - Assist in writing an agreement with a pharmaceutical company - Assist in developing a monitoring plan

Study Name: The Fragility Fracture Trial
Version No: 2
Date: 2020-10-04
EudraCT No: 2019-004766-17

Acronyms and Abbreviations

Acronym/Abbreviation	Explanation
AE	Adverse event
DSUR	Data safety update report
eCRF	Electronic case report form
EudraCT	European Union Drug Regulating Authorities Clinical Trials Database
EQ-5D-3L	EuroQol-5 Dimensions-3 Levels
EQ-5D-5L	EuroQol-5 Dimensions-5 Levels
GCP	Good clinical practice
ICD-7-SE	International Classification of Diseases, 7 th revision, Swedish Version
ICD-10-SE	International Classification of Diseases, 10 th revision, Swedish Version
ICH	International Conference/Council on Harmonisation of Technical Requirements for Registration of Pharmaceuticals for Human Use
ICMJE	International Council of Medical Journal Editors
ID	Identification
NA	Not applicable
ND	Not done
NK	Not known
SEK	Swedish Krona
SUSAR	Suspected unexpected serious adverse reaction

Study Name: The Fragility Fracture Trial
Version No: 2
Date: 2020-10-04
EudraCT No: 2019-004766-17

1. Synopsis

Background: The incidence of fracture is high among older adults, and older adults who sustain one fracture are at high risk of sustaining new fractures. No clinical trial has examined whether bone-protective therapy is effective in preventing new fractures among older adults with a recent non-hip, non-vertebral fragility fracture (i.e., a fracture due to a fall from standing height or less), without prior measurement of bone mineral density.

Primary objective: To investigate whether zoledronic acid (a widely used antiresorptive) reduces the risk of new clinical fractures, as compared with placebo, in older adults with a recent non-hip, non-vertebral fragility fracture.

Study design: 4-year, phase IV, multicenter, parallel-group, randomized, double-blind, placebo-controlled trial.

Study population: Adults aged 65 or older with a non-hip, non-vertebral fragility fracture in the past 2 years. Fragility fracture is defined as a fracture occurring after a fall from standing height or less.

Number of participants: 2900.

Investigational products: Two infusions of zoledronic acid (5 mg) or placebo, one at baseline and one at 24 months. Prior to infusion, participants will receive a loading dose of oral vitamin D (50,000 IU or 2.5 mg). Participants will also be prescribed monthly oral vitamin D (25,000 IU or 1.25 mg/month) for the duration of the trial.

Primary outcome: Time to first new clinical fracture.

Study period: Q1 2021 - Q1 2027.

Study Name: The Fragility Fracture Trial
Version No: 2
Date: 2020-10-04
EudraCT No: 2019-004766-17

2. Introduction

About 95,000 individuals suffered a major fracture in Sweden in 2017.^{1,2} In comparison, less than half that number, about 40,000, suffered a stroke or myocardial infarction.¹ The most serious type of fracture is the hip fracture, which is regarded as an end stage disease because 25% of hip fracture patients die within a year.^{3,4} Of surviving hip fracture patients, only a minority regain their pre-fracture level of physical functioning and quality of life.⁵ High mortality rates and reduced quality of life are also seen in patients with vertebral fractures.^{6,7} Thus, hip and vertebral fractures are serious threats to the health and independence of older people.

Despite the seriousness of hip and vertebral fractures, these do not constitute the majority of fractures, as they occur in about 28,000 persons per year in Sweden.^{1,2} Far more common are fractures of the arm or lower leg, which occurred in about 58,000 people in Sweden in 2017.^{1,2} Furthermore, according to government data we have on hand, individuals with a previous fracture of the arm or lower leg have 2.6 times the risk of sustaining a fracture as do individuals without a previous fracture. The data also show that fractures of the arm and lower leg occur at a mean age of 71 years, compared to 77 years for vertebral fractures and 83 years for hip fractures. These facts suggest that health care professionals may be able to prevent hip and vertebral fractures by targeting interventions to older adults with a non-hip, non-vertebral fracture.

Bone-protective agents, such as bisphosphonates, are currently available for reducing fracture risks in older adults.⁸ However, the efficacy of these agents after a fracture has not been studied in clinical trials other than after a hip or vertebral fracture.⁹ Most trials have recruited participants on the basis of osteoporosis or low bone density (with or without a vertebral fracture),⁹ but this approach has the disadvantage that physicians often have limited access to bone densitometry,¹⁰ which complicates treatment decisions in clinical practice. Furthermore, many fracture patients, especially male fracture patients, do not have osteoporosis. The actual percentage of patients who have osteoporosis varies among studies, but hip or spine osteoporosis (T-score ≤ -2.5) has been reported to be present in 36%,¹¹ 44%,¹² and 56%¹³ of female fracture patients and in 13-15%¹¹ and 21%¹² of male fracture patients. Another study, which examined appendicular osteoporosis (T-score ≤ -2.5 in the heel, finger, or forearm), showed that osteoporosis was present in 18% of women with an osteoporotic fracture.¹⁴ Another difficulty in fracture prevention is that health care systems often are not organized to identify patients with osteoporosis. Whereas fractures are initially treated at emergency wards, bone densitometry is usually located in other departments (if available at all) and primary care is often responsible for making treatment decisions.

Given the high incidence of non-hip, non-vertebral fractures, the high risk of recurrent fractures, and the seriousness of hip and vertebral fractures, which occur later in life than other types of fractures, it would be of high interest to study whether bone-protective therapy is effective in older adults who are selected solely for having a history of non-hip, non-

Study Name: The Fragility Fracture Trial
Version No: 2
Date: 2020-10-04
EudraCT No: 2019-004766-17

vertebral fracture, without prior assessment of bone mineral density. Increased treatment of this patient group is feasible because only around 10% of Swedish fracture patients aged 50 or older receive treatment.^{15,16}

Zoledronic acid is a well-known and well-studied bone-protective agent, which was approved in the European Union in 2005.¹⁷ Zoledronic acid reduces bone resorption and belongs to the bisphosphonate class.¹⁸ In three large clinical trials, zoledronic acid was shown to reduce the risk of clinical fracture in women with osteoporosis, in women with osteopenia, and in men and women with a hip fracture.^{19–21} Although a fourth trial conducted in men with osteoporosis did not show a significant effect of zoledronic acid on clinical fractures, this trial was smaller and it did show a significant effect on radiologically detected vertebral fractures.²²

The most common adverse effects of zoledronic acid are transient post-infusion symptoms (pyrexia, myalgia, headache, arthralgia, and influenza-like symptoms), which occur in about one third of patients in the first 3 days following an initial infusion.¹⁹ These symptoms are less common after subsequent infusions.¹⁹ Zoledronic acid and other bisphosphonates have been associated with two rare but serious adverse effects: atypical femoral fractures and osteonecrosis of the jaw.^{23,24} However, osteonecrosis of the jaw does not primarily occur in osteoporosis patients but in cancer patients, who receive much higher doses of zoledronic acid to reduce the adverse skeletal effects of cancer (e.g., bone metastases).²³ In osteoporosis patients, the incidence of osteonecrosis of the jaw is estimated to be 1 in 100,000 to 1 in 10,000.²³ Atypical femoral fractures are also rare, and they are typically reported after long treatment periods of 7 or more years.^{25,26} It should also be noted that no increased risk of these adverse events was reported in the four largest trials of zoledronic acid that have been conducted to date.^{20–22,26}

3. Objectives

3.1. Primary objective

The primary objective is to investigate whether zoledronic acid reduces the risk of new clinical fractures, as compared with placebo, in older adults with a recent non-hip, non-vertebral fragility fracture.

3.2. Secondary objectives

The secondary objectives are to investigate whether zoledronic acid, as compared with placebo:

1. has a different effect on new clinical fractures in men and women
2. reduces the risk of cancer
3. reduces the risk of cardiovascular disease (stroke or myocardial infarction)

Study Name: The Fragility Fracture Trial
Version No: 2
Date: 2020-10-04
EudraCT No: 2019-004766-17

4. reduces the risk of death
5. reduces the risk of falling

Although it is conventional to designate subgroup analyses as exploratory, the subgroup analysis by sex was designated as a secondary objective because no clinical trial has shown that bone-protective therapy significantly reduces clinical fractures in men.⁸ This fact may explain part of the low rates of osteoporosis treatment in men.^{16,27} Cancer was selected as a secondary outcome to confirm the results of a recent phase IV trial, which showed a significant reduction in cancer (a pre-specified safety outcome) in osteopenic women treated with zoledronic acid.²¹ Cardiovascular disease was selected because both clinical trial data and observational data have suggested that bisphosphonates protect against stroke and myocardial infarction.^{21,28-30} Death was selected to confirm the results of a phase III trial that demonstrated significantly reduced mortality in hip fracture patients treated with zoledronic acid.²⁰ Falling was selected as an outcome to confirm the results of two trials, one of denosumab and one of zoledronic acid, which showed significant reductions in falls.^{20,31}

3.3. Exploratory objectives

The exploratory objectives are as follows:

1. To investigate whether the effect of zoledronic acid on new clinical fracture decreases with age
2. To investigate the time-to-onset of effect of zoledronic acid on clinical fractures
3. To investigate whether a higher level of physical activity leads to a greater reduction in clinical fractures with zoledronic acid
4. To investigate whether zoledronic increases muscle strength, as compared with placebo
5. To investigate whether the effect of zoledronic acid on new clinical fractures is greater in participants who have a higher 10-year probability of major osteoporotic fracture according to the FRAX fracture risk assessment tool
6. To investigate whether zoledronic acid reduces height loss, as compared with placebo
7. To investigate whether zoledronic acid improves health-related quality of life
8. To investigate whether zoledronic acid reduces the risk of death, cancer, clinical fractures, and cardiovascular disease, as compared with placebo, over 10 years

Efficacy by age was selected as an exploratory objective because some researchers suggest that bone-protective therapy is less effective in the oldest age groups, perhaps because the high incidence of falls offsets beneficial skeletal effects.^{32,33} Low treatment rates of osteoporosis have also been observed in the oldest age groups.³⁴ Efficacy by level of physical activity was selected because it is well known that bone-protective agents have different effects on bone mineral density in different individuals. Given that physical loading decreases the risk of fractures and is necessary for maintaining bone health at all ages,³⁵ we hypothesize that zoledronic acid will result in a greater increase in bone density, and therefore a greater decrease in fracture risk, in participants who are physically active. Muscle strength is included as an explanatory outcome because it is a possible mechanism for a beneficial effect of zoledronic acid on falls. This mechanism is supported by the known crosstalk between osteocytes and muscle cells, which is mediated by pathways influenced by bone-protective

Study Name: The Fragility Fracture Trial
Version No: 2
Date: 2020-10-04
EudraCT No: 2019-004766-17

agents.³⁶ Height loss was selected because it is related to efficacy concerning vertebral fractures. Height loss was designated as an exploratory outcome because it will only be assessed halfway through the trial and not at the end. A reduction in height loss with zoledronic acid was observed in two previous trials of zoledronic acid.^{19,21} Health-related quality of life will be used to assess whether participants perceive any health benefits from zoledronic acid treatment. Health-related quality of life outcomes were specified in the protocol of three previous trials of zoledronic acid.²⁰⁻²² The results of one of these trials have been published,³⁷ and these showed a significant improvement in the EuroQol-5 Dimensions-3 Levels (EQ-5D-3L) visual analogue scale, in which respondents rate their overall health on a scale from 0 to 100 (from worst to best imaginable health). An improvement was not, however, observed in the summary score of the 5 dimensions.³⁷

4. Trial Design

The study will be a 4-year, phase IV, multicenter, parallel-group, randomized, double-blind, placebo-controlled trial. A 4-year duration was selected because this is anticipated to capture the greatest anti-fracture efficacy of 2 infusions of zoledronic acid administered at baseline and at 24 months (see Section 6). The trial will be multicenter so that a sufficient number of participants can be recruited. Study centers (one per principal investigator) will be located in major hospitals in Sweden. We anticipate that approximately 10 centers will be needed. A parallel-group, randomized, and double-blind design was selected to enable the study to produce substantial confirmatory evidence of efficacy. The trial will be placebo controlled because there is currently no standard treatment for fracture patients who do not have a hip or vertebral fracture and who have not undergone bone densitometry.

The study is anticipated to take 6 years to complete. Participants will be recruited during the first 2 years, starting in the first quarter of 2021 and ending in the last quarter of 2022. The remaining 4 years will be spent monitoring participants until they have each completed 4 years of follow-up. The last participant's last follow-up contact is planned for the first quarter of 2027. The last participant's last follow-up contact is defined as the End of the Trial.

5. Eligibility Criteria

5.1. Inclusion criteria

To be included in the trial, patients must meet all of the following criteria:

1. Willing and able to provide written informed consent
2. Age ≥ 65 years
3. Ambulatory (i.e., able to walk without the assistance of another person; canes, walkers, and other assistive devices are permitted)

Study Name: The Fragility Fracture Trial
Version No: 2
Date: 2020-10-04
EudraCT No: 2019-004766-17

4. Community dwelling (i.e., living in own home or with friends or relatives)
5. Sustained a non-hip, non-vertebral fragility fracture in the past 2 years

Fragility fractures are defined as fractures occurring after a fall from standing height or less.¹⁰ In particular, these falls include the following International Classification of Diseases, 10th Revision, Swedish Version, (ICD-10-SE) codes:

- 1) Fall on same level involving ice and snow (W00)
- 2) Fall on same level from slipping, tripping and stumbling (W01)
- 3) Other fall on same level due to collision with, or pushing by, another person (W03)
- 4) Fall while being carried or supported by other persons (W04)
- 5) Other fall on same level (W18)

If the type of fall is unknown, it will be assumed *not* to have occurred after a fall from standing height or less.

Non-hip, non-vertebral fractures will include fractures of the clavicle, upper arm, forearm, ribs, pelvis, femur (excluding hip), or lower leg. Fractures of the face, skull, hands, and feet will be excluded, because these are not generally considered osteoporotic.¹⁰

The limit of no more than 2 years since fracture is based on two considerations. The first consideration is that the risk of sustaining a new fracture is highest soon after the initial fracture.^{38,39} For this reason, we expect zoledronic acid to have the greatest effect if it is administered as soon as possible. However, setting a short limit would reduce the number of potentially eligible participants, making the trial more difficult to carry out. Therefore, the time limit should not be set too short for pragmatic reasons.

A minimum duration between time of fracture and time of recruitment has not been set, because no delay in fracture healing was observed in a phase III trial of zoledronic acid in hip fracture patients.²⁰

5.2. Exclusion criteria

Patients will be excluded from the trial if they meet any one of the following criteria:

1. History of hip fracture or vertebral compression fracture
2. Undergone bone density scanning since the fragility fracture
3. Severe renal impairment (estimated glomerular filtration rate of <35 ml per minute per 1.73 m² of body surface area)
4. Remaining life expectancy of <1 year, according the investigator's judgement
5. Hypocalcemia (serum calcium <2.2 mmol/L)
6. Sarcoidosis (contraindication for vitamin D)

Study Name: The Fragility Fracture Trial
Version No: 2
Date: 2020-10-04
EudraCT No: 2019-004766-17

7. Previous use of bone-protective drug (e.g., bisphosphonate, teriparatide, denosumab, raloxifene, or strontium ranelate; calcium and vitamin D are acceptable)
8. Use of systemic glucocorticoids at a dose of ≥ 5 mg (prednisolone or equivalent) for ≥ 3 months in the past year
9. Other medication or medical condition for which bone-protective therapy is indicated (e.g., bone metastases or use of aromatase inhibitor; osteoporosis is permitted)

Patients with a hip or vertebral fracture will be excluded because these patients should receive bone-protective therapy according to current Swedish national guidelines.⁴⁰ Patients who have undergone bone density scanning will be excluded because the inclusion of these patients could skew the study population toward low-risk patients who do not qualify for treatment according to current guidelines, which would reduce the statistical power of the trial.

6. Investigational Products

Zoledronic acid (5 mg) or placebo (normal saline) will be given as a 15-minute intravenous infusion at baseline and at 2 years. The volume of fluid will be 100 ml (5 ml of zoledronic acid or placebo + 95 ml of mannitol, sodium citrate, and water for injections). A flush of 10 ml of normal saline will be given before and after administration, resulting in a total of 120 ml of intravenously infused fluid. All patients will receive advice about nutrition and exercise to prevent new fractures.

Zoledronic acid can cause post-infusion symptoms (pyrexia, myalgia, headache, arthralgia, or influenza-like symptoms) within the first 3 days.¹⁹ Patients will be informed that these symptoms may be uncomfortable but that they are not dangerous and can be eased with paracetamol if needed.

To prevent hypocalcemia, all participants will receive a loading dose of oral vitamin D (50,000 IU or 2.5 mg) 1 week before the first infusion. Participants will also be prescribed monthly oral vitamin D (25,000 IU or 1.25 mg/month), which is to be taken for the duration of the trial. Participants who have not taken their monthly vitamin D will receive a second loading dose 1 week before the second infusion. The sponsor will cover the cost of the loading doses, but participants will be expected to cover the cost of their monthly vitamin D.

The monthly dosage frequency of vitamin D is less frequent than was used in the phase III trials of zoledronic acid.^{19,20} A monthly frequency was, however, used successfully in a large phase IV trial.²¹ Calcium will not be prescribed because this phase IV trial provided only vitamin D, with successful results.²¹ If a participant has not received the loading dose of vitamin D between 1 and 4 weeks before the day of randomization, then both randomization and the first infusion will be delayed until this criterion is met.

The above-mentioned dose and administration route for zoledronic acid were selected based on the design of previous phase III trials and on standard use in clinical practice.^{17,19,20} The treatment interval of 2 years is not standard, however, as 1-year intervals were used in the

Study Name: The Fragility Fracture Trial
Version No: 2
Date: 2020-10-04
EudraCT No: 2019-004766-17

phase III trials and are commonly used in clinical practice.^{17,19,20} Our decision to extend the treatment interval is based on evidence from a phase IV trial that found similar efficacy with 18-month treatment intervals.²¹ A smaller trial also demonstrated that the effect of zoledronic acid on bone mineral density peaks at least 24 months after an initial infusion.⁴¹ Furthermore, a post-hoc analysis of two large clinical trials demonstrated similar reductions in clinical fractures in patients who had received only 1 instead of 3 infusions of zoledronic acid.⁴² Based on these findings, we expect a 24-month interval to be optimal.

Zoledronic acid and placebo must be stored securely, meaning that it is accessible only to authorized persons and that it is kept in the conditions specified in the Summary of Product Characteristics for Aclasta (the brand name of zoledronic acid).¹⁷ The drugs may only be used for the purposes specified in this protocol. At the end of the study, any remaining products will be handed over to pharmacies for destruction. A drug accountability log will be used to follow the pathway of the study medications throughout the study. At the time of writing, we have not decided on a manufacturer for zoledronic acid and placebo.

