15.5. Medical record registration

In accordance with Swedish regulations,⁶⁷ investigators must register in participants' medical records that the participants are involved in a clinical trial. These entries must include the following information:

1. The trial is randomized and double-blind.
2. The investigational products are zoledronic acid and placebo (normal saline), given as two intravenous infusions at a dose of 5 mg with two years in between.
3. Monthly oral vitamin D (25,000 IU or 1.25 mg/month) has been prescribed, and a loading dose of vitamin D (50,000 IU or 2.5 mg) has been given.
4. Written informed consent has been obtained.
5. Participant ID code.
6. Medication number of the received investigational product.
7. Instructions for emergency unblinding.
8. Investigational product received (once unblinded).

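### The vitamin D doses are stated in IU and in mg as if equal, but the two figures differ by a factor of two, for the loading dose and the monthly dose alike

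*Protocol*

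**What the plan says.** Section 6 gives the purpose of the supplement, "To prevent hypocalcemia, all participants will receive a loading dose of oral vitamin D", and sets the loading dose: "all participants will receive a loading dose of oral vitamin D (50,000 IU or 2.5 mg) 1 week before the first infusion". It then sets the maintenance dose: "Participants will also be prescribed monthly oral vitamin D (25,000 IU or 1.25 mg/month), which is to be taken for the duration of the trial".

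The synopsis repeats both pairs, the monthly one as "Participants will also be prescribed monthly oral vitamin D (25,000 IU or 1.25 mg/month) for the duration of the trial". Section 15.5 lists what investigators must enter in each participant's medical record. The list includes the same monthly pair and the statement that "a loading dose of vitamin D (50,000 IU or 2.5 mg) has been given".

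Other sections depend on these doses:

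- Section 6 postpones randomization and the first infusion until the loading dose has been received within a set window.
- Section 9 makes a second loading dose depend on whether monthly intake was sufficient in the investigator's opinion.
- Section 13.5 counts participants who take vitamin D at the required monthly dose.

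**The concern.** Each dose is given twice, with the IU and mg figures joined by *or* as though they were the same amount. They are not. A prescriber working from mg and one working from IU would order amounts that differ twofold. The protocol names no vitamin D product or strength and does not say which unit prevails, so a site cannot settle the question from the document. It is also not something a statistical analysis plan would settle, because the dose is protocol content.

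The vitamin D has a safety function here. It is given to limit hypocalcemia after zoledronic acid, and Section 6 deliberately prescribes no calcium. Planned serum calcium samples are taken only at screening and one week before the 24-month visit (Section 12.3 and Table 1). No scheduled sample soon after an infusion would show that too little had been given. Reactions to too much would also be less visible, because Section 8.3 leaves reactions to non-investigational products, vitamin D among them, out of the definition of an adverse drug reaction.

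The monthly product is prescribed and the participant pays for it, across about 10 centers. The protocol describes no common supply that would fix the monthly dose in practice.

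**Working it through.** **Inputs from the protocol** (synopsis, Section 6 and Section 15.5, identical in all three):

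- Loading dose: 50,000 IU, also given as 2.5 mg.
- Monthly dose: 25,000 IU, also given as 1.25 mg.

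**Assumption.** 1 IU of vitamin D = 0.025 microgram, that is, 40,000 IU per mg. This is the definition of the unit, but the protocol does not state it.

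**Step 1: the conversion that the protocol implies.**

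- Loading: 50,000 IU / 2.5 mg = 20,000 IU per mg, or 0.05 microgram per IU.
- Monthly: 25,000 IU / 1.25 mg = 20,000 IU per mg, or 0.05 microgram per IU.

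Both pairs use the same conversion, which is half the number of IU per mg that the definition gives. This points to one wrong conversion factor applied throughout. Because the pairs are identical in three places, it is not a fault in reading the PDF.

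**Step 2: mg from IU**, with mg = IU × 0.025 / 1000.

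- Loading: 50,000 × 0.025 / 1000 = 1.25 mg (stated 2.5 mg; ratio 2.5 / 1.25 = 2.0).
- Monthly: 25,000 × 0.025 / 1000 = 0.625 mg (stated 1.25 mg; ratio 1.25 / 0.625 = 2.0).

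**Step 3: IU from mg**, with IU = mg × 1000 / 0.025.

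- Loading: 2.5 × 1000 / 0.025 = 100,000 IU (stated 50,000 IU).
- Monthly: 1.25 × 1000 / 0.025 = 50,000 IU (stated 25,000 IU).

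**Step 4: the two readings side by side.**

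| Dose | If the IU figure is meant | If the mg figure is meant |
|---|---|---|
| Loading | 50,000 IU = 1.25 mg | 100,000 IU = 2.5 mg |
| Monthly | 25,000 IU = 0.625 mg | 50,000 IU = 1.25 mg |
| Monthly dose per day (÷ 30.44 days) | about 820 IU | about 1,640 IU |

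If IU is intended and a site follows mg, the participant gets double. If mg is intended and a site follows IU, the participant gets half. For whichever figure is intended, the error runs in one direction only.

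**The case against.** The arithmetic is hard to dispute; the case on the other side is about consequence.

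1. **A factor of two for all 2900 participants is a ceiling.** Misdosing needs someone to act on the unintended unit. IU comes first wherever the doses appear, and a product labelled only in IU would make an error unlikely. This stands. The figure of 2900 counts those exposed to the ambiguity and does not forecast dosing errors.
2. **The trial's inference is not affected.** Vitamin D is non-investigational and prescribed identically in both blinded arms. The treatment comparison, the event count and the power are unchanged. This also stands, and the point is not one of bias.
3. **There are other safeguards against hypocalcemia.** Serum calcium below 2.2 mmol/L excludes a patient at entry (Section 5.2) and bars the second infusion unless it is resolved in time (Section 6.1). This stands in part. Those tests come before the infusions and do not replace the loading dose. The protocol gives no data on whether either candidate dose would be inadequate or harmful, and no such claim is made here.
4. **The randomization condition concerns timing.** Section 6 asks that the loading dose has been received in its window and describes no check of the amount. The mismatch therefore does not change who is randomized, although it leaves unclear what counts as the loading dose.
5. **Only part of the adherence analysis is touched.** In Section 13.5 the descriptive count at the required monthly dose has no single reference. Complete adherence, which Fisher's exact test compares between groups, is defined by use at every contact.

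None of this reconciles the figures or tells a prescriber which one to follow.

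**Conclusion.** The concern holds: the doses are wrong as written. Under the standard definition of the unit, which is the only assumption, the IU and mg figures differ by exactly 2.0 for both the loading and the monthly dose, in all three places where they appear. Participants can therefore be given or prescribed half or double the intended amount. How many would be depends on how the product is labelled and which unit sites use, and the protocol does not say.

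The efficacy comparison is not biased. The point still has to be corrected, because this is an operative dose of a drug that the protocol requires for every participant, all aged 65 or older, for a safety reason. The same error would also be carried into each participant's medical record, where other clinicians would read it. The document does not show which figure is intended, and this review takes no view on that.

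**What to change.** - Decide the intended doses against the product to be supplied. Then state one unit, or two that agree, in the synopsis, Section 6 and Section 15.5. If the IU figures are right, the mg figures become 1.25 mg (loading) and 0.625 mg (monthly). If the mg figures are right, the IU figures become 100,000 IU and 50,000 IU.
- Carry the corrected dose into the medical-record entry, any prescription templates and the eCRF. Section 12.2 says that the eCRF had not yet been created, so it can be built with the right figure.
- Let the required monthly dose in Section 13.5 refer to the corrected figure.
- Tell the sites which figure governs.

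The cost is a correction in three places and a notice to sites. If the correction changes the dose that sites are to give, the sponsor should check whether it counts as a substantial amendment under Section 15.3, which would need approval first. No change to the design, sample size or efficacy analysis follows.
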